2. STUDY OBJECTIVES

2.1 Primary Objective:

To compare EUS guide fine needle biopsy versus fine needle aspiration for whole exome sequencing and genomic profiling in tissue sampling of pancreatic solid tumors.

2.2 Secondary Objectives:

- To compare the DNA yield of FNB versus FNA in tissue sampling of pancreas cancer including sufficient DNA to complete un-amplified whole exome sequencing.
- To compare the number of needle passes necessary to obtain adequate tissue sample to make a cytological/histological diagnosis when FNB is used as compared to the conventional FNA for pancreas cancer
- To compare the histology quality of the specimens obtained via FNB as compared to conventional FNA.
- To compare the yield of tissue sufficient for targeted (Foundation Medicine Assay) genomic profiling of pancreas tumors.
- To estimate the safety profile of FNB as compared to conventional FNA. (by historical comparison)
- Per needle adequacy for cytology

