8.2 Study Protocol

- 1) Filling the “Pre-Procedure Patient Registration” section of the “Registration and Data Collection” form
- 2) Review of the signed informed consent before the start of procedure.
- 3) All patients will undergo conscious sedation or Monitored Anesthesia Care (MAC) for the duration of the procedure. Conscious section and/or MAC are the standard method of sedation for all patients that have EUS at our institution, unless contraindicated.
- 4) Morphologic features of the lesion will be examined and documented in the procedure report. Based on the location and type of the lesion, the participating endosonographer determines the necessity of performing an FNA. If FNA deemed necessary, the patient will be included in the study.

- 5) Randomization of needle order. The first needle to be used will be selected by randomization using block randomization in envelopes (FNA first, FNB first) by tumor location (1 block for head tumors, 1 block for body/tail tumors).
- 6) Conventional FNA will be alternated with FNB (22 gauge for all sites) in the usual fashion for obtaining histological material. A minimum of 2 passes (1 with each needle) will be obtained from all lesions. Conventional FNA will be performed with a standard 25g needle (our standard needle) in the usual fashion using back and forth passes for 30 seconds. Negative pressure will be applied for both needle types using the “capillary” technique of withdrawing the stylet slowly (5-10cm per second) during the to and fro movement of the needle. All FNA material will be expressed onto a glass slide. Visible core samples will be removed and placed in formalin after an initial “touch prep” (light touch of tissue to slide). The presence or absence and length (in mm) of grossly visible each core will be recorded by the cytotechnologist/study personnel. Standard passes (alternating with each needle) will be repeated in pairs until an adequate sample is obtained or the endoscopist feels that no further sampling is warranted. Then, a 2nd and 3rd set of passes (one with each needle) will be performed to collect material for biobanking and DNA and RNA extraction. The sample will be expressed into a sealed biospecimen container and flash frozen in liquid nitrogen, then stored at -80C. If no material is obtained, the research pass will be repeated up to a maximum of 2 passes for each needle.

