- 7) After each pass of needle, the on-site cytotechnologist will evaluate the adequacy and the degree of the pathological changes in the obtained material. Based on the information provided by the cytotechnologist, the endosonographer will repeat the FNA until enough material is obtained to confirm the clinical diagnosis. The initial determination of adequacy will be made by the onsite cytotechnologist. The final determination of cytological adequacy will be made by the study pathologist (AN) based on the criteria below.
- 8) Separate sets of slides and formalin jars will be produced in the GI suite from the tissue obtained from each type of the needle. Each pass will be placed on separate slides and

formalin jars with labelling (A, B). 9) In order for the pathologist to remain blinded of the needle type that the tissue was obtained with, two separate slide sets will be generated and each set will be labeled as “*Slide Set A or B*”. Slides that are prepared from the FNB will be labeled as “*Slide Set B*” depending on the parity of the assigned SNI number. Slides that are prepared from the conventional FNA needle will be labeled as “*Slide Set A*” to complete each pair 10) Pathology interpretation for clinical purposes will be done by the on-call pathologist of the day, using all material available. For study purposes a single study pathologist (AN) will interpret all of the slides. The pathologist will evaluate the slides for cell quantity (adequate vs. scanty/acellular), grade of dysplasia (atypical vs. malignant cells), and presence of core samples.

11) Each slide set (A or B) will be evaluated and reported separately for research purposes and accumulatively to generate the patient’s pathology report for medical records.

12) Quarterly, the available data will be reviewed retrospectively and the rate of anticipated complications will be calculated. Anticipated complications of EUS with FNA include, but are not limited to post-procedure pancreatitis, bleeding, perforation, and infection. Serious adverse events from FNA are rare but include life threatening events, inpatient hospitalization, prolongation of existing hospitalization or any unanticipated complication including death as a result of the procedure will be reported to Mayo Clinic IRB.

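### Gross core length has no blinded reading, and histology quality, the secondary comparison it could be used for, has no stated metric

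*Combined protocol and SAP*

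**What the plan says.** Section 2.2 lists as a secondary objective "To compare the histology quality of the specimens obtained via FNB as compared to conventional FNA". The synopsis names per-needle adequacy for histology among its specific aims, and section 9.1 refers to histology yield per sample. None of these says which variable carries the comparison.

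Section 8.2 describes how core tissue is recorded and read:

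- Item 6: besides whether a core is present, "length (in mm) of grossly visible each core will be recorded by the cytotechnologist/study personnel". Visible cores are taken out and put in formalin after a touch preparation. The same item has the two needles alternate in pairs.
- Item 7: "After each pass of needle, the on-site cytotechnologist will evaluate the adequacy". The study pathologist then makes the final decision on cytological adequacy.
- Item 8: "Separate sets of slides and formalin jars will be produced in the GI suite from the tissue obtained from each type of the needle".
- Item 9 introduces the slide-set labels with this purpose: "In order for the pathologist to remain blinded of the needle type that the tissue was obtained with".
- Item 10: a single study pathologist interprets all slides for cell quantity, grade and the presence of core samples. Length is not on the list.

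**The concern.** The hypothesis is that the core needle yields better tissue. Deciding at the bedside whether a strand is a core, and where it begins and ends, involves judgement. A recorder who knows the needle may resolve doubtful cases in the expected direction, without intending to. Length in millimetres is the only numeric core measure in the plan and has no blinded counterpart. Because histology quality has no defined metric, nothing stops the bedside length from becoming the reported comparison. Under section 9.1 a continuous variable would go to a paired t-test at the two-sided 5% level, and that test cannot separate observer bias from a true difference.

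**Working it through.** **Who reads what (section 8.2)**

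| Measure | At the procedure | Blinded study pathologist |
|---|---|---|
| Cytological adequacy | yes, initial (item 7) | yes, final (items 7 and 10) |
| Core presence | yes (item 6) | yes (item 10) |
| Core length, mm | yes (item 6) | no |

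Only length lacks a blinded reading.

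**Do the bedside staff know the needle?** No sentence says so. The cytotechnologist is on site, assesses material after every pass while the needles alternate, and works where slides and jars are sorted by needle type. No masking is described for this person. Knowledge of the needle is a strong inference.

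**Is the pathologist's reading independent of the bedside call?** Not fully. Item 6 sends only visible cores to formalin, so the bedside judgement decides what can later be read as core tissue.

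**Does the label conceal the needle?** Under item 9, FNB becomes set B depending on the parity of the patient identifier, while FNA becomes set A with no such condition. Taken literally, A always means FNA. If parity sometimes makes FNB set A, both sets carry the same label unless FNA switches too. The remark about completing each pair suggests that a switch was intended, but the rule does not say so.

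**The plan's own figure.** Section 9.1 claims at least 80% power for McNemar's test with 50 pairs. The exact two-sided test gives 81.2% (difference 25%, discordance 38%) and 80.8% (difference 20%, discordance 25%), so the claim reproduces. It concerns DNA adequacy and has no bearing on this point beyond checking the method.

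**Illustration for core presence, not length.** From section 9.1: 50 pairs, two-sided 5%. Assumed, with no source in the documents: a true core rate of 60% for both needles, independence within pairs, a fraction f of coreless FNB passes called cores, and a fraction m of FNA cores missed.

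- Recorded rates: FNA = 0.6(1 − m); FNB = 0.6 + 0.4f. Spurious difference = 0.6m + 0.4f.
- With m = f = 0.10: FNA 0.54, FNB 0.64. Discordant pairs: FNB only 0.64 × 0.46 = 0.2944; FNA only 0.54 × 0.36 = 0.1944; total 0.4888.
- Rejection probability = the sum, over the number of discordant pairs D ~ Binomial(50, 0.4888) and the FNB-only count among them ~ Binomial(D, 0.2944/0.4888), of all outcomes with exact p ≤ 0.05.

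| Errors assumed | Spurious difference (points) | Significant in |
|---|---|---|
| none | 0 | just under 3% |
| f = 10 / 15 / 20%, m = 0 | 4 / 6 / 8 | 4.3 / 6.1 / 8.9% |
| f = m = 5% | 5 | 5.1% |
| f = m = 10 / 15 / 20% | 10 / 15 / 20 | 12.1 / 25.1 / 43.4% |

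**Length.** The documents give no mean or standard deviation for core length, so no bias in millimetres can be derived. In standardised terms only, assume no true difference and an observer bias of 0.2, 0.3 or 0.4 standard deviations of the paired difference. The non-centrality is the bias times √50, that is 1.41, 2.12 or 2.83 on 49 degrees of freedom, and the paired t-test is significant in 28%, 55% or 79% of trials. These rates follow wholly from the assumed bias and are not estimates for this trial.

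**The case against.** The strongest reply is that length is not a declared endpoint. Item 6 says only that it is recorded, no analysis is assigned to it by name, and the readings made for study purposes are those of the blinded pathologist. Treating bedside length as descriptive would already fit the current text. This stands, and it limits the point to a gap that should be closed.

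A reader might infer that an unmasked bedside record contradicts the single-blinded label. It does not. Item 9 identifies the pathologist as the blinded party, an operator handling two different needles cannot be masked, and recording gross yield on the spot is ordinary practice.

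A reader might also take the 43% as the size of the problem. The documents do not support that. The figure concerns core presence, which does have a blinded reading, and it needs two errors in opposite directions at the top of an assumed range. With false FNB cores alone the result is 4 to 9%.

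Lastly, blinded measurement on formalin sections could reject strands wrongly called FNB cores, but could not recover FNA cores that were never put in formalin. This also stands, and it is why the remedy needs a common bedside definition.

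**Conclusion.** The point holds in limited form. Gross core length is recorded by staff for whom no masking is described and who very likely know the needle. No blinded person measures it, and section 2.2 leaves histology quality without a metric, so the unblinded length is open to use as one.

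The effect is confined to a secondary objective. DNA sufficiency is set at 1.1 µg and read by spectrophotometer (section 8.2 item 13), and the sample size rests on DNA adequacy (section 9.1); neither uses core length. It would go too far to say that the plan makes unblinded length its histology endpoint, or that core presence has no blinded reading.

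No size can be given for length from the documents. The figures for presence, 4 to 9% with one error and 12 to 43% with both at 10 to 20%, illustrate assumed error rates only. The change is worth making because it is cheap, not because a large bias has been shown.

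**What to change.** 1. In sections 2.2 and 9.1, name the histology-quality metric and base it on the study pathologist's blinded reading of the coded material: core presence, plus total core length in millimetres on the formalin sections.
2. In section 8.2 item 6, state that bedside core presence and length are descriptive only, and state in the protocol who is masked and who is not.
3. Write one definition of a visible core and apply it identically to both needles, since this call decides what reaches formalin.
4. Reconcile item 9 so that the parity condition governs both needles' labels and the label conceals the needle. Step 1 depends on this.

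The cost is one extra measurement by a reader who already interprets all the slides, plus protocol wording; no patient has an added procedure. Two limits remain. Length after processing differs from fresh length, though this applies to both needles. FNA cores not placed in formalin stay outside the blinded measurement; the common definition can reduce that loss but not remove it.

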5. INTRA AND POST- PROCEDURE EVALUATION

5.1 Evaluations during Procedure

Standard monitoring, including continuous cardiopulmonary evaluations, will be performed during the EUS exam. In case of immediate complications, including but not limited to, visceral perforation or extensive bleeding, the procedure will be terminated and appropriate standard care will be provided. The precise time for each FNA procedure as defined by the first puncture attempt to the completion of expressing the cytologic material on the glass slide and formalin.

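### Paired diagnostic passes with one common stop make the two needles' pass counts equal by design, so the secondary objective on passes needed has to be given a per-needle endpoint and a censoring rule

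*Combined protocol and SAP*

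**What the plan says.** Section 2.2 lists as a secondary objective "To compare the number of needle passes necessary to obtain adequate tissue sample to make a cytological/histological diagnosis" with FNB as against conventional FNA.

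Section 8.2, item 6, sets the sampling scheme. "A minimum of 2 passes (1 with each needle) will be obtained from all lesions". After that, "Standard passes (alternating with each needle) will be repeated in pairs until an adequate sample is obtained", or until "the endoscopist feels that no further sampling is warranted". Both limbs of the stop apply to the two needles together. The passes for DNA and RNA come afterwards as separate sets.

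Item 7 adds: "After each pass of needle, the on-site cytotechnologist will evaluate the adequacy". It has sampling repeated "until enough material is obtained to confirm the clinical diagnosis", without mentioning pairs or a particular needle. Item 8 keeps the material apart: "Each pass will be placed on separate slides and" in separate jars. Items 10 and 11 have the clinical reading use all the material together, and the study reading done by slide set, that is, by needle.

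Section 8.1 lets the endoscopist switch to another needle if two passes in total have not given an adequate sample. Section 9.1 names a paired t-test for continuous variables and chi-square or Fisher tests for categorical ones. It does not mention pass counts or censoring.

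**The concern.** The objective concerns how many passes each needle would need. The design fixes how many passes each needle receives, and makes that number the same for both. A count of passes performed therefore carries no information about the needles.

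What can be learned instead depends on a point the plan leaves open, namely whose material must be adequate before sampling stops. There are three readings: either needle, both needles, or the pooled material. Items 7, 10 and 11 describe material that accumulates over passes, which points to a patient-level stop. Under such a stop, the number needed by the slower needle is often never seen.

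Section 1.4 mentions a possible saving in passes as a proposed advantage of FNB. Without a definition and an analysis, the trial may have nothing usable to say about it.

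**Working it through.** **The plan's own figure.** Section 9.1 claims at least 80% power for McNemar's test on DNA adequacy with 50 patients, two-sided 5%. The exact binomial McNemar test gives 81.2% for a 25-point difference with 38% discordant (31.5% against 6.5%), and 80.8% for 20 points with 25% discordant (22.5% against 2.5%). The claim reproduces and is not in question here. No figure is given for pass counts.

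**Step 1: passes performed.** If sampling stops after k complete pairs, FNA passes = k and FNB passes = k, so the difference is 0 in every patient. The standard deviation of the differences is 0 and t = 0/0. No assumed rate is needed. Stopping within a pair would shift a count by at most one pass, depending on needle order.

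**Step 2: either-needle stop.** Let A and B be the first adequate FNA and FNB pass. Sampling stops at min(A, B), so both are observed only when A = B: complete cases always tie. With independent passes and per-pass adequacy pA and pB,

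P(FNA censored) = pB(1 − pA) / [1 − (1 − pA)(1 − pB)], and symmetrically for FNB.

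The documents give no per-pass rates; those below are assumptions. For 60/80%: 0.8 × 0.4 / (1 − 0.4 × 0.2) = 0.32/0.92 = 34.8% for FNA, and 0.6 × 0.2 / 0.92 = 13.0% for FNB. The true mean difference is 1/0.6 − 1/0.8 = 1.67 − 1.25 = 0.42 passes.

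| FNA/FNB | True difference | Counted difference | FNA censored | FNB censored |
|---|---|---|---|---|
| 50/80% | 0.75 | 0 | 44.4% | 11.1% |
| 60/80% | 0.42 | 0 | 34.8% | 13.0% |
| 60/90% | 0.56 | 0 | 37.5% | 6.2% |
| 70/90% | 0.32 | 0 | 27.8% | 7.2% |

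With a shared patient effect (normal on the logit scale, SD 1 or 2, same marginal rates), FNA is censored in 27.6-46.5% and FNB in 2.5-10.9%.

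**Step 3: both-needles stop.** Assume a cap of 5 pairs, no needle change and no discretionary stop. Under independence FNA is censored in (1 − pA)^5: 0.5^5 = 3.1%, 0.4^5 = 1.0%, 0.3^5 = 0.2%. Averaged over the shared effect, the range is 2.1-9.6% (SD 1) and 7.1-19.4% (SD 2).

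**Step 4: pooled stop.** Sampling may end when neither needle alone is adequate, so both numbers can be censored. The rates in step 2 treat adequacy as a property of a single pass and do not carry over. The zero in step 1 does.

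**Step 5: first-pass adequacy, exact McNemar, 50 patients.** For 60/80% under independence the discordant shares are 0.8 × 0.4 = 32% and 0.6 × 0.2 = 12%.

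| FNA/FNB | Independence | SD 1 | SD 2 |
|---|---|---|---|
| 60/80% (20 points) | 49.8% | 57.0% | 68.8% |
| 70/90% (20 points) | 63.3% | 68.4% | 78.3% |
| 50/80% (30 points) | 84.1% | 89.8% | 96.1% |
| 60/90% (30 points) | 92.0% | 95.0% | 98.2% |

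The Wald 95% interval half-width is 13.0-17.7 points over these 12 cases.

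**Step 6: a censored analysis under the either-needle stop.** Kaplan-Meier mean passes restricted to 5, FNA minus FNB, at 60/80%: 0.40 against a true 0.40 under independence, 0.63 against 0.49 (SD 1), 0.83 against 0.59 (SD 2). Over all four scenarios with a shared effect the overstatement is 0.14-0.36 passes.

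**The case against.** The best reply is that the data are there. Adequacy is judged after each pass and material is kept by pass, so a per-needle first adequate pass can be derived, and 9.1 never says that the t-test will be run on passes performed. This stands in part: a reader might infer that the objective cannot be answered at all, and item 7 does not support that. But no section defines the endpoint or says what to record for a needle still inadequate at the stop.

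A reader might also infer that the trial would report a false finding of no difference. With every difference zero the test cannot be computed, so the failure would show itself. The loss is an unanswered objective.

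Third, if both needles must be adequate, the problem may seem to vanish. Censoring does fall, but the 0.2-3.1% in step 3 needs independent passes and leaves out the discretionary stop and the needle change. With lesions that are hard for both needles it reaches 7.1-19.4% at the larger assumed effect. Passes performed still tie.

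Finally, first-pass adequacy replaces the stated quantity and does not estimate a number of passes. That is true. It is proposed as the main analysis because the adequacy-driven stop cannot censor it, while the analysis that does estimate passes rests on an assumption that is probably wrong.

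**Conclusion.** The point holds. Where item 6 is followed, passes performed are equal for the two needles in every patient, and the generic paired t-test on them is undefined. This follows from the design alone. How far the numbers needed are censored depends on the unstated meaning of adequacy and on assumed rates: about 28-44% for FNA and 6-13% for FNB with an either-needle stop and independent passes, less with a both-needles stop, and not quantified for a pooled stop.

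A reader might extend this to the main comparison. The documents do not support that: DNA comes from separate research passes, and the power statement in 9.1 reproduces. One secondary objective is affected, and the plan should be amended for it.

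**What to change.** - Do not apply the paired t-test to pass counts.
- Main analysis: adequacy of each needle's first diagnostic pass, by exact McNemar test with a confidence interval for the paired difference, in all patients who received one diagnostic pass with each needle. Item 6 plans this for everyone. The exception is a complication under 5.1, where "the procedure will be terminated and appropriate standard care will be provided"; report how many. Use the on-site judgement in item 7, the only adequacy stated to be made after each pass. Item 9 describes blinding of the pathologist and is silent on the on-site assessor, so say whether that person knows the needle.
- Supportive analysis: passes to first adequate sample per needle, by a paired method that censors a needle not adequate at the stop or at a needle change. Label it as resting on independent censoring, which shared lesion difficulty makes doubtful.
- State which of the three meanings of adequacy in item 6 applies.
- Confirm that pass number is recorded with needle; the Appendix A form was not available to check.
- The needle-change wording in 8.1 and the paired scheme in item 6 must be reconciled.

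The cost is a short definition and two small analyses, with no added passes. First-pass adequacy ignores later passes. Its power for a 20-point difference with 50 patients is about 50-63% under independence and 57-78% with the assumed shared effect, so the interval should be reported and a non-significant result not read as equivalence.

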7.5 Confidentiality of Subject Data

The Investigator will ensure that the confidentiality of the patients' data will be preserved in a safe database. The patients will not be identified by their names, but by SNI, which consists of their initials and number in the study.

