7.6 Standardized Numerical Identifier (SNI)

Each subject will be assigned an identifier that will be used for identification purposes. SNI consists of the patient's initials, a ten digit number that correlates with the date and time of the procedure and the initials of the participating investigator in the following format:

I	I	I	M	M	D	D	Y	Y	H	H	M	M	I	I	I
---	---	---	---	---	---	---	---	---	---	---	---	---	---	---	---

Patient initial

Date

Time

Inv. Initial

8. STUDY DESIGN:

This is a single-center, prospective randomized controlled trial. All male and female patients 18 years old or older that are referred for evaluation of pancreatic solid mass can be considered for this trial.

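### The slide-labelling rule in section 8.2, item 9 does not protect the study pathologist's blinding: as printed the letters are fixed to the needles, and the parity clause is incomplete

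*Combined protocol and SAP*

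**What the plan says.** The synopsis calls the trial single blinded. Section 8.2 sets out the masking of the slide reads:

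- Item 8 separates the material by needle and pass, using slides and "formalin jars with labelling (A, B").
- Item 9 gives the purpose: "In order for the pathologist to remain blinded of the needle type that the tissue was obtained with". It then sets the letters: FNB slides are Set B "depending on the parity of the assigned SNI number. Slides that are prepared from the conventional FNA needle will be labeled as" Set A, with no condition attached to the FNA letter.
- Item 10 has one study pathologist read every slide for cell quantity, grade of dysplasia and presence of cores. Item 7 gives the same person the final decision on cytological adequacy.

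The SNI, whose parity item 9 invokes, is described twice. Section 7.5 says it is an identifier "which consists of their initials and number in the study". Section 7.6 says it is the patient's initials, "a ten digit number that correlates with the date and time of the procedure", and the investigator's initials.

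The documents do not say who holds the code, whether the SNI appears on the slides, or whether the reader is kept from either.

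**The concern.** A masking code works only if the reader cannot get from the label to the needle. Item 9 prints a label that maps one-to-one to the needle and adds a parity condition that changes nothing. The code is in the protocol itself, and the Steering Committee page lists a pathologist. Names are removed, so it is only an inference that this is the study reader, but a reader with access to the protocol is likely.

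Per-needle adequacy for cytology and for histology are specific aims 3 and 4 in the synopsis, and section 2.2 lists cytology adequacy and histology quality as secondary objectives. They depend on judgement calls by one person, with no second reader described. The trial's hypothesis is that FNB is superior, so any expectation effect has an obvious direction. For these outcomes item 9 is the only masking step described.

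**Working it through.** **Reading 1: the item as printed.** FNB goes to Set B and FNA to Set A. No case is given in which FNB becomes Set A. So P(FNB | Set B) = 1 in every pair. A balanced letter with a concealed key would give 0.5.

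**Reading 2: a parity swap was intended.** The instruction lacks two things.

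1. The mapping. Nothing says whether odd or even gives B for FNB.
2. The number. Under 7.5 it is the patient's number in the study. Under 7.6 the format is MMDDYYHHMM, that is 2 + 2 + 2 + 2 + 2 = 10 digits, so the last digit belongs to the minute of the procedure. A patient with an odd study number whose procedure falls on an even minute gets opposite parities under the two sections.

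Even with both supplied, the key would be deterministic, and anyone who knows the rule and sees the SNI could read it.

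**What an unblinded reader could do (illustration only).** The documents give no discordance rate for cytology or histology and no size for reader bias, so both are assumed. The plan also has no figure of its own to reproduce on this point.

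- n = 50 pairs (section 3.1); two-sided 5% level (section 9.1).
- The needles are truly equal: a proportion d of pairs is FNB-only adequate and d is FNA-only adequate.
- Reader expectation moves a proportion s of all pairs from concordant to FNB-only adequate, so the discordant probabilities become (d + s, d). A 5% shift is 0.05 × 50 = 2.5 pairs on average.
- The number of discordant pairs M is Binomial(50, 2d + s). Given M = m, the FNB-only count K is Binomial(m, (d + s)/(2d + s)).
- The uncorrected McNemar test rejects when |2K − m|/√m ≥ 1.96. The exact test rejects when the two-sided Binomial(m, 0.5) p-value is ≤ 0.05. Rejection probabilities are summed over all m and K.

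False-positive rate, %, shown as exact / uncorrected:

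| d (each way) | s = 0 | s = 2% | s = 5% |
|---|---|---|---|
| 5% | 0.9 / 4.7 | 2.0 / 6.4 | 6.9 / 13.2 |
| 12% | 2.4 / 4.4 | 3.1 / 5.3 | 6.1 / 9.4 |
| 20% | 3.0 / 5.3 | 3.3 / 5.9 | 5.2 / 8.6 |

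At d = 8% and 16% the rates lie between these rows, or within 0.1 point of them, for s = 2%, and between them for s = 5%. Over all five values of d, a 2% shift gives at most 6.4% (uncorrected) and 3.4% (exact).

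Section 9.1 names McNemar only in the power statement for DNA adequacy. It is used here because the data are paired, not because the plan assigns it to the slide reads.

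**The case against.** The strongest reply is that this is a drafting slip. The word parity, and the choice of A or B earlier in item 9, suggest that a swap was intended. Under a completed swap, masking would be adequate as long as the reader does not see the SNI or does not know the rule, and section 8.1 ties the SNI to identification and data entry in the study database, not to slide labels. The letter is only a mask, so its being non-random matters less than it would for allocation, and needle order is randomized separately by envelope. The 7.5 wording may be shorthand for the fuller format in 7.6. The affected outcomes are secondary, the analysis promised for them is mainly descriptive, and item 14 ties pathology data collection to published cytopathology guidelines, which gives the judgements some structure. Finally, item 6 says "Visible core samples will be removed and placed in formalin after an initial" touch preparation, and presence of cores is one of the reads, so the tissue itself may reveal the needle whatever the label says.

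Much of this stands. A swap was probably meant, the DNA outcome that sizes the trial is untouched, and no relabelling can guarantee masking. The illustration rests on assumed inputs, and the exact test's rise from 0.9% partly reflects its conservatism when few pairs are discordant. But probable intent does not tell GI-suite staff which letter to write, and no other section supplies the mapping, the key holder or concealment of the SNI. That tissue may sometimes give the needle away is no reason for the label to do so every time.

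**Conclusion.** The concern holds. As printed, item 9 defeats its own purpose; read charitably, it cannot be carried out. Masking of the slide reads is unprotected. The documents do not show that it is broken, because they do not say that the reader is given the code or sees the SNI.

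The reach is limited to the single reader's outcomes: cytological adequacy, dysplasia grade and presence of cores. DNA quantity and the 1.1 ug sufficiency criterion are spectrophotometer measurements and do not depend on slide labels. The inflation in false positives ranges from slight at a 2% shift to roughly two- to threefold for the uncorrected test at a 5% shift (8.6/5.3 = 1.6 to 13.2/4.7 = 2.8), all under assumed discordance and bias. The conclusion rests on the text of item 9 and does not need these figures.

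**What to change.** Replace the labelling rule in item 9 as follows:

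- Draw a random letter for each patient (FNB is A or B with probability 1/2) and place it in the existing needle-order envelope from item 5.
- Use that letter on all slides and formalin jars from that needle.
- Have existing study staff other than the reader hold the key until the study reads are locked.
- Keep the SNI and any needle information off the material the study pathologist sees.
- Delete the parity clause, and give the SNI one definition in sections 7.5 and 7.6.

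The cost is one extra line per envelope, a small labelling step in the GI suite and a wording change; no extra patients, passes or tests are needed. Item 11 uses the same slide sets for the medical-record report, so clinical identifiers may have to be covered for the study read, which adds some handling. Masking may remain partial because of visible cores, and the report should say so.
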